- **Target lesions:** Target lesions should be identified and measured at baseline. Target lesions include measurable lesions up to a maximum of two lesions per organ and up to five lesions in total that are representative of all involved organs. Target lesions should be selected on the basis of their size (lesions with the longest diameter) and are to undergo reproducible repeated measurements. If the largest lesion does not lend itself to reproducible measurement it should not be considered a target lesion and instead the next largest lesion that can be measured reproducibly should be selected. A sum of the longest diameters for all target lesions will be calculated and reported as the baseline sum diameters. The baseline sum diameters will be used as reference to further characterize any objective tumor regression in the measurable dimension of the disease.
- **Non-target Lesions:** All other lesions (or sites of disease) including any measurable lesions over and above the 5 target lesions should be identified as non-target lesions and should also be recorded at baseline. Measurements of these lesions are not required, but the presence, absence, or in rare cases unequivocal progression of each should be noted throughout follow-up.

7.3 Definitions of Disease Response

Definition of response in target lesions:

- **Complete Response (CR):** Disappearance of all target lesions
- **Partial Response (PR):** At least a 30% decrease in the sum of the diameters of target lesions, taking as reference the baseline sum diameters
- **Progressive Disease (PD):** At least a 20% increase in the sum of the diameters of target lesions compared to baseline sum of target lesions, or any new lesions
- Stable Disease (SD): Neither sufficient decrease to qualify as a PR or sufficient increase to qualify as PD

Response should be confirmed by repeat CT scan that may be performed at the next regularly scheduled scan and no earlier than 4 weeks after imaging showing a particular response (unless clinically indicated).

Definition of response in non-target lesions:

- Complete Response (CR): Disappearance of all target lesions
- Progressive Disease (PD): Appearance of one or more new lesions and/or unequivocal progression of existing non-target lesions
- Incomplete Response/Stable Disease (SD): Persistence of one or more non-target lesions

The response to immunotherapy may differ from the typical responses observed with cytotoxic chemotherapy including the following:

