- Response to immunotherapy may be delayed
- Response to immunotherapy may occur after PD by conventional criteria
- The appearance of new lesions may not represent PD with immunotherapy
- SD while on immunotherapy may be durable and represent clinical benefit.

Modification of RECIST as described will discourage the early discontinuation of an immune checkpoint inhibitor and provide a more complete evaluation of its anti-tumor activity than would be seen with conventional response criteria.

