7.4 Evaluation of Overall Response

The primary endpoint of this study is best Overall Response Rate (ORR) that is determined from the start of treatment until 6 months later (Table 2). Best ORR will depend on the status of both target and non-target disease as well as whether new lesions appear. Furthermore, it is defined as the best response at all time points. When SD is the best response it must also meet protocol specified minimum time from baseline of 8 weeks. If the minimum time is not met when SD is the best time point response, then the subject's best response depends on the subsequent assessments. For example, if SD is the best response at first assessment, and has PD at the second assessment but does not meet the minimum duration of SD will have best response of PD.

Target Lesions	Non-Target Lesions	New Lesions	Overall Response
CR	CR	No	CR
CR	PR/SD	No	PR
PR	Non-PD	No	PR
SD	Non-PD	No	SD
PD	Any	Yes or No	PD
Any	PD	Yes or No	PD
Any	Any	Yes	PD

Table 3. Best Overall Response Criteria

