7.5 Verification Scans

Confirmation of CR or PR is required (Table 3). Confirmed CR or PR will be claimed only if the criteria for each are met at a subsequent time point (minimum 4 weeks after criteria for an objective response are first met).

Confirmation of PD is required if PD is equivocal. If repeat scan confirms PD, then PD will be claimed using the date of the initial scan. If repeat scan does not confirm PD, then PD will not be claimed.

Overall Response At First Time Point	Overall Response At Second Time Point	Best Overall Response
CR	CR	CR
CR	PR	SD, PD, OR PR*
CR	SD	SD provided minimum criteria for SD duration met, otherwise, PD
CR	PD	SD provided minimum criteria for SD duration met, otherwise, PD
CR	NE	SD provided minimum criteria for SD duration met, otherwise, NE
PR	CR	PR
PR	PR	PR
PR	SD	SD
PR	PD	SD provided minimum criteria for SD duration met, otherwise, PD
PR	NE	SD provided minimum criteria for SD duration met, otherwise, NE
NE	NE	NE

Table 4. Best Overall Response When Confirmation of CR and PR is Required.

CR = complete response, PR = partial response, SD = stable disease, PD = progressive disease, NE= not evaluable.

*If CR is achieved at first time point, but any disease including PR at subsequent time point will result in PD. Best response would depend on whether minimum duration for SD was met. Sometimes CR may be claimed when subsequent scan suggests small lesions were likely still present and the patient had PR, not CR at first time point. If this is the case, then the original CR should be changed to PR and the best response is PR.

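### Section 7.3 measures target-lesion progression from the baseline sum, so a partial responder's targets must regrow at least 71% from their smallest sum before PD is called by size, which can lengthen DOR and PFS

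*Combined protocol and SAP*

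**What the plan says.** Section 7.3 sets partial response (PR) at a target sum at least 30% below baseline. It sets target-lesion PD at "At least a 20% increase in the sum of the diameters of target lesions compared to baseline sum of target lesions", or any new lesion. Section 7.2 gives the baseline sum one role, as the reference for regression, and nothing in 7.2 to 7.5 refers to the smallest sum reached. Section 7.3 ends with the statement "Modification of RECIST as described will discourage the early discontinuation of an immune checkpoint inhibitor", but the features of immunotherapy response listed just before it do not mention the progression reference. Section 10.1 names RECIST 1.1 for the primary endpoint without mentioning any modification.

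The surrounding rules are these:

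- Section 7.4: "Best ORR will depend on the status of both target and non-target disease as well as whether new lesions appear", and "it is defined as the best response at all time points". Table 3 scores target CR with non-target PR/SD as overall PR.
- Section 7.5: "Confirmed CR or PR will be claimed only if the criteria for each are met at a subsequent time point", and "Confirmation of PD is required if PD is equivocal". Table 4 scores PR followed by PD as "SD provided minimum criteria for SD duration met, otherwise, PD". Its footnote says "If CR is achieved at first time point, but any disease including PR at subsequent time point will result in PD", unless the CR is re-read as a PR.
- Section 2: PFS ends at PD or death, and DOR ends at PD. Section 10.1 ends DOR at progression or death.
- The section on additional radiation to non-target lesions counts palliative radiation there as progression.
- Imaging: Table 2 (note 3) and the list in 7.1 give 8-weekly scans for the first 26 weeks. Section 3 and the opening of 7.1 give the same interval with no end.

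**The concern.** With the threshold tied to baseline, the fall in the target sum does not lower the level at which progression is called. The deeper the response, the more regrowth is tolerated before the size criterion is met. Section 2 uses the terms that 7.3 defines, so the natural reading is that 7.3 governs the end of both DOR and PFS. DOR is the more exposed of the two, because every partial responder starts from a sum at or below 70% of baseline. The trial has a single arm, so there is no comparator scored by the same rule against which to read a longer DOR or PFS.

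The documents also leave open whether the baseline reference is meant. The closing statement of 7.3 does not name it, and 10.1 mentions no modification.

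**Working it through.** **Inputs.** PD at 1.20 × baseline and PR at 0.70 × baseline or less (Section 7.3). Scheduled scans at weeks 8, 16 and 24 within the 26-week window (Section 7.1, Table 2). Design rates of 5% and 15%, 52 patients, and early-stopping probability 0.55 (Section 10.2). The plan gives no figure for regrowth from nadir, so there is none to reproduce.

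**Regrowth needed.** With baseline 100, the regrowth needed as written is 120/nadir − 1. A smallest-sum rule would call PD at 1.2 × nadir.

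| Nadir | PD by size as written | PD by size, smallest-sum | Regrowth needed as written |
|---|---|---|---|
| 90 | 120 | 108 | 33% |
| 80 | 120 | 96 | 50% |
| 70 | 120 | 84 | 71% |
| 50 | 120 | 60 | 140% |
| 40 | 120 | 48 | 200% |

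A PR has a nadir of 70 or less, so 71% is the minimum for any partial responder.

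**Direction.** The smallest sum, baseline included, never exceeds baseline, so 1.2 × smallest sum ≤ 1.2 × baseline. Any scan that meets the written rule also meets the smallest-sum rule, so PD by size can only come at the same time or later as written. The two rules agree when the sum never falls below baseline.

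**Effect on the scheduled scans.** Take 100 → 50 → 50 → 80 at weeks 8, 16 and 24. Under a smallest-sum rule, 80 exceeds 60 and PD is dated at week 24. As written, 80 is below 120 and no PD is recorded. If imaging stops at 26 weeks, the event becomes a censored time.

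**Number of responders.** With all 52 enrolled, 52 × 0.05 = 2.6 and 52 × 0.15 = 7.8. At a 5% rate, allowing for early stopping, expected enrolment is 30 + 22 × (1 − 0.55) = 39.9, which gives about 2 responders.

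**Primary endpoint.** Take 100 → 50 → 65. As written, 65 is at or below 70, so the PR is confirmed. With a smallest-sum reference, 65 exceeds 60, so the sequence is PR then PD, which Table 4 scores as SD or PD. If the next scan must confirm, a difference needs 1.2 × nadir ≤ 70, that is, a nadir of at most 70/1.2 = 58.3. The confirming scan must lie between 1.2 × nadir and 70. It also requires that no response counts after PD.

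**Reappearing targets.** After an overall CR, target regrowth 0 → 10 is PD by the Table 4 footnote, unless the CR is re-read as a PR. After target CR with persisting non-target disease (overall PR in Table 3), 0 → 115 is not PD by size, since 115 is below 120. The documents do not say whether a reappearing target counts as a new lesion.

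**The case against.** The strongest reply is that 7.3 is explicit and can be applied as it stands. The closing statement of 7.3 aims to avoid early discontinuation, and a baseline reference is consistent with that aim. DOR and PFS are secondary, single-arm Kaplan-Meier summaries with no decision rule attached. New lesions, unequivocal non-target progression, palliative radiation and, for PFS, death can end the interval first, and confirmation of equivocal PD may narrow the difference.

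Much of this stands. It limits the effect to patients whose sum fell below baseline and who progress by target regrowth alone, and it means that a deliberate choice cannot be excluded. It does not show that the choice was made.

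A reader might infer more than the documents support:

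- *That 7.3 contradicts its own criteria.* The content of RECIST 1.1 is not in the documents. The Table 4 footnote covers only an overall CR. Table 5 does use nadir for irPD, but it belongs to a separate criteria set and is only a contrast.
- *A delay in weeks.* If the sum is assumed to double every 8 to 24 weeks, the delay is T × log2(100/nadir): 4.1 to 12.3 weeks at nadir 70 and 8 to 24 at nadir 50. The doubling time is not in the documents. Slower regrowth would exceed these figures, and 8-weekly scans would coarsen them, so they are neither estimates nor upper limits.
- *Wider inflation of the response rate.* A path such as 70 → 85 → 68 might look like an extra response as written, but Table 4 scores PR then SD as SD. Section 7.3 also allows that response may follow conventional PD, and 7.4 takes the best response over all time points. The condition that no response counts after PD is therefore not settled.

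**Conclusion.** The concern holds for endpoint scoring. As written, every partial responder needs at least 71% regrowth from the smallest sum before PD by size. PFS, and DOR in patients who respond under both rules, can only be equal or longer than with a smallest-sum reference. The regrowth percentages follow from the text alone. That 7.3 governs DOR and PFS is the natural reading of Section 2, but it is not stated.

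The size of the effect on median DOR or PFS cannot be derived. Much of it may be progression events turned into censoring, because the scheduled scans are listed only to 26 weeks. The primary endpoint can change only in narrow cases such as 100 → 50 → 65, and only if no response counts after PD. The number of such patients is unknown. Each would add one response against the bound of 6 in 52, but no type I error inflation is shown.

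**What to change.** For scoring ORR, DOR and PFS, define target-lesion PD as an increase of 20% or more over the smallest sum on study, baseline included. If the baseline reference is intended, say so, justify it, and report DOR and PFS under the smallest-sum reference as well. State how a reappearing target lesion is scored after target CR with persisting non-target disease.

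Two separate wording repairs belong in the same amendment. Align the DOR definition in Section 2 with 10.1, so that death also ends it. Remove irSD from the response sentence in 7.6, which otherwise conflicts with the irORR definition of irCR or irPR just before it.

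PD also bears on continuation of the checkpoint inhibitor and on withdrawal (Section 3, the end of 7.3, and 9.1). The sponsor must reconcile those passages with the endpoint definition; no treatment rule is proposed here.

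The cost is wording, using measurements already taken, plus that reconciliation check, without which the protocol would carry two PD definitions. DOR and PFS may look slightly less favourable.

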2. STUDY OBJECTIVES

Primary endpoint

• To evaluate best overall response rate (ORR) in non-irradiated lesion(s).

Secondary endpoints

- To evaluate ORR as defined by immune-related response criteria (irRC) in non-irradiated lesion(s).
- To evaluate duration of response (DOR) from the time CR or PR is first determined until the first date of documented progressive disease.
- To evaluate overall survival (OS) from the start of radiation therapy of the first lesion to the date of death for any cause.
- To evaluate progression free survival (PFS) from the start of radiation therapy of the first lesion to the date of progressive disease or death for any cause.
- To evaluate treatment-related adverse events.

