5.2 Radiation Therapy

The intent of RT in this study is to augment a cancer-specific immune response when given with ICI. As such, while RT is commonly and effectively used to treat symptomatic lesions in metastatic cancer patients, the presence of symptomatic lesions is not a requirement for RT to be given in this study.

Appropriate subjects will have at least 3 measurable lesions to be eligible for this study, 2 of which would receive RT and at least 1 that would not.

Day 1 of the study will be considered the day that the first fraction of radiation is delivered to the first lesion. This should be no more than 10 calendar days after enrollment.

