7. TREATMENT RESPONSE EVALUATION

7.1 Imaging Assessment

All subjects will have a CT scan of the chest, abdomen, and pelvis with IV and oral contrast to assess treatment response every 2 months. Patients with iodine/contrast allergy should receive premedication according to institutional standard of care prior to receiving contrast. Patients with known brain metastases should have an MRI of the brain with contrast every 2 months or sooner

as medically indicated. Diagnostic scans should be performed with no larger than 5 mm slice thickness.

Diagnostic imaging studies as described above should be obtained at each of the following intervals, or sooner if clinically indicated:

- Baseline/screening
- 8 weeks (+/-2 weeks) after initiation of radiation therapy to the first lesion
- Every 8 weeks (+/-2 weeks) thereafter for the first 26 weeks after initiation of radiation therapy

Additional sites of disease not encompassed by the studies described above should be imaged according to the schedule above using the most appropriate diagnostic imaging modality according to the treating physician's discretion.

7.2 Definitions for Disease Assessment

- **Measurable lesions:** Lesions that can be accurately measured in at least one dimension with longest diameter at least 10 mm on CT scan; lymph nodes must measure at least 15 mm in short axis
- **Non-measurable lesions:** All other lesions <10 mm on CT scan, or lymph nodes <15 mm in short axis. Other non-measurable lesions include: ascites, pleural or pericardial effusion, lymphangitic involvement of skin or lung, abdominal masses not measurable by reproducible imaging techniques.

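### Section 7.3 sets no minimum absolute increase for size-based PD, so if progression is scored on one small non-irradiated lesion, a 2 mm rise can count as a PFS event

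*Combined protocol and SAP*

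**What the plan says.** - **PD rule (7.3).** Target-lesion PD is "At least a 20% increase in the sum of the diameters of target lesions compared to baseline sum of target lesions", or any new lesion. No minimum in millimetres appears here or elsewhere. Table 3 in 7.4 turns target-lesion PD directly into overall PD.
- **Smallest scored lesion (7.2).** A non-nodal lesion is measurable with "longest diameter at least 10 mm on CT scan"; for nodes, "lymph nodes must measure at least 15 mm in short axis". Target lesions are "up to a maximum of two lesions per organ and up to five lesions in total".
- **Number of lesions (4.1, 5.2).** At least three measurable lesions are needed, "2 of which would receive RT and at least 1 that would not".
- **Lesion set (2, 10.1).** ORR and the irRC response rate are limited to non-irradiated lesions. PFS runs "to the date of progressive disease or death for any cause" and carries no such limit; neither does DOR. Section 7.2 does not remove irradiated lesions from the target set.
- **Confirmation (7.5).** PD needs a repeat scan only if it is equivocal, and an unconfirmed PD is then dropped. Equivocal is not defined.
- **Criteria.** Section 10.1 names RECIST 1.1 for the primary objective. Section 7.3 ends by speaking of a modification of RECIST.

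**The concern.** A purely relative threshold shrinks with the lesion. In a small scored sum, 20% is a few millimetres, and ordinary variation between two readings of an unchanged tumour can reach it. Each such reading may be recorded as a PFS event. DOR ends on the same definition. The trial has one arm, so a Kaplan-Meier curve shortened by reading error has no comparator subject to the same error. The rule also sits awkwardly with the aim in 7.3 of not abandoning immunotherapy before a delayed response can appear.

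**Working it through.** **1. Plan figures.** The plan gives no event count, power or false-PD rate for PFS, so there is nothing to reproduce on this point. As background, the two-stage rule (30 then 52 patients, stop at 1 or fewer responses, reject at 6 or more) gives exact type I error 0.043, power 0.802 and early-stopping probability 0.554. The plan states 0.05, 0.80 and 0.55. These count responses and do not depend on the PD threshold.

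**2. Rise that triggers PD** = 0.20 × baseline sum.
- One 10 mm lesion: 0.20 × 10 = 2 mm.
- One 15 mm node: 0.20 × 15 = 3 mm.
- All target lesions, all in one organ (at most two scored): 2 × 10 = 20 mm; 0.20 × 20 = 4 mm.
- All target lesions, two or more organs (at least three scored): 3 × 10 = 30 mm; 0.20 × 30 = 6 mm.

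**3. Where a 5 mm minimum would change anything.** 5 / 0.20 = 25 mm. It matters only for scored sums below 25 mm: always for one 10 mm lesion, possibly for an all-target sum in a single organ, never for an all-target sum across two or more organs.

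**4. DOR.** A responder's sum is at most 0.70 × baseline, and PD needs at least 1.20 × baseline. The gap is at least 0.50 × baseline, which is 5 mm for a 10 mm lesion. With the baseline reference, DOR is therefore less exposed than PFS.

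**5. Illustrative false PD.** Simulation of one lesion whose true size does not change. Baseline and three follow-up readings have independent normal error with SD s. The baseline reading must be at least 10 mm. PD is called if (follow-up − baseline) / baseline ≥ 0.20. Three scans correspond to 8-weekly imaging over the first 26 weeks (7.1). The values of s are assumptions.

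| True size | s = 0.5 mm | s = 1.0 mm | s = 1.5 mm |
|---|---|---|---|
| 10 mm | 0% | 1.6% | 7.3% |
| 12 mm | 0.3% | 11.7% | 23% |
| 15 mm | 0.02% | 6.5% | 21% |
| 20 mm | 0% | 1.4% | 9.9% |

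Entries are the chance of at least one false PD call. The 10 mm row is lower than the 12 mm row because only baseline readings of 10 mm or more are kept. That discards the low readings which would make a later rise look large.

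- With a 5 mm minimum added, every cell is at most 2.4%.
- If PD must instead be seen on two consecutive scans, every cell is at most 5.5%.
- Three unchanged 12 mm lesions (sum 36 mm) give about 0.5% to 3.2% at s = 1.0 to 1.5 mm, with or without the 5 mm condition.

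**The case against.** **PFS is not said to rest on one lesion.** Only the response endpoints are limited to non-irradiated disease. Section 7.2 picks the largest reproducibly measurable lesions, and patients have at least three. If PFS uses the ordinary target set, the 2 mm case cannot arise. This stands, and it makes the point conditional. It does not remove it, because the plan leaves the PFS lesion set open.

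**Confirmation offers some protection.** A borderline 2 mm change is a natural candidate for equivocal PD, and 7.3 also asks in general terms for a repeat CT to confirm response. This stands in part. If every PD were confirmed, the rates would fall to at most 5.5%. But 7.5 limits the duty to equivocal PD without defining it, so a reading that meets the 20% rule can be accepted on one scan.

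**The error rates are assumed.** True. At s = 0.5 mm none exceeds 0.3%.

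**PFS is a descriptive secondary endpoint** with no hypothesis or power. True; this limits the weight of the point.

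Stronger readings that the documents do not support:
- *A 2 mm change is below imaging resolution.* The plan says "Diagnostic scans should be performed with no larger than 5 mm slice thickness". That is an upper limit on slice thickness, not the error of an in-plane diameter.
- *Small scored sums will be common.* The plan gives no distribution of lesion number or size.
- *A spurious PD will end immunotherapy.* Section 3 continues ICI until progression, but 9.1 ties withdrawal to confirmed PD plus the investigator's judgement of no benefit. These two passages must be reconciled. No clinical rule is proposed here.

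**Conclusion.** The gap is real and its reach is conditional. Applied as written, 7.3 lets a 2 mm rise in a single scored 10 mm lesion count as PD, and no other section reliably prevents it. It affects PFS mainly and DOR less. A 5 mm minimum would matter only for scored sums below 25 mm.

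Its size depends on two things that the documents do not settle: which lesions are scored for PFS, and the reading error. Under single-lesion scoring and s between 0.5 and 1.5 mm, false PD over three scans ranges from about 0% to 23%. A reader might infer that the rule ends PFS early for patients in general, or that it undermines the primary test. Neither follows: all-target sums of 25 mm or more would be unchanged by a 5 mm minimum, and the Simon figures do not use the PD threshold. This is a worthwhile, inexpensive clarification of secondary endpoints.

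**What to change.** 1. In the 7.3 PD definition, require a minimum absolute increase in the sum of diameters as well as the 20% rise, measured from the same reference. A minimum of 5 mm is used here as an example. The value should be set to agree with the RECIST 1.1 criteria named in 10.1, whose text the protocol does not reproduce. Keep new lesions and unequivocal non-target progression as PD.
2. State in Section 2 or 10.1 which lesions are scored for PFS and DOR: non-irradiated lesions only, or all target lesions.
3. Define equivocal PD in 7.5, so that it is clear when a repeat scan is required.
4. Reconcile Section 3 with 9.1 on what progression means for continued treatment.

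Item 1 is one phrase and the others are a sentence or two each; sample size and schedule do not change. The price is that true growth of 2 to 4 mm in a small lesion may be called one scan later.
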